9.5 Follow up of AE/SAE/DAR/DAE/SUSAR

Any AE/SAE/DAR/DAE/SUSAR observed from randomization up to the end of the study will be followed up to resolution. Resolution means that the subject has returned to a baseline state of health or the Investigator does not expect any further improvement or worsening of the AE.

9.6 Data Monitoring Committee

According to the EMEA GUIDELINE ON DATA MONITORING COMMITTEES (January 2006) a Data Monitoring Committee (DMC) is an external group of independent experts assessing the progress, safety data and efficacy endpoints of this clinical study. [...]

10 QUALITY CONTROL

[...]

11 STATISTICS

11.1 Sample Size Calculation

We analyzed preliminary data on Cyp-A which showed an increase of 0.27 over six months (Nardo, G. et al. 2011). With 142 patients enrolled, we will have 80% power to detect a 44% decrease in the rate of progression in Cyp-A at a two sided $p=0.05$ significance level. This assumes a drop-out rate of 1.75% per month (10% over the study). The calculation is based on the method shown in (<http://hedwig.mgh.harvard.edu/biostatistics/node/42>). For the other biomarkers we only had data on the between patient variation and not on the within patient variation which could be used for calculating sample size for the proposed study. Usually the within patient variation is less than the between patient variation, so power calculated using the between patient variation is conservative. The T-reg values were assessed in slowly progressing vs. rapidly progressing ALS43 and the estimated difference was used as the difference expected to slow the progression of the disease in patients receiving RNS60. A total of 128 patients is needed to detect a difference in means of 0.25 units between the two treatment arms at 24 weeks with a standard deviation (SD) of 0.5. Similar assumptions were made for the other biomarkers for which, except for Actin-NT (that would require 1542 patients), numbers range from 8 to 68 (Nardo, G. et al. 2009; Nardo, G. et al. 2011; Henkel, J. et al. 2013; Chiò A. et al., 2011):

- MCP-1: a total of 16 patients is needed to detect a difference in means of 220 units between the two treatment arms at 24 weeks with a standard deviation (SD) of 140;
- Actin-NT: a total of 1542 patients is needed to detect a difference in means of 0.1 units between the two treatment arms at 24 weeks with a standard deviation (SD) of 0.7;
- 3-NT: a total of 24 patients is needed to detect a difference in means of 50 units between the two treatment arms at 24 weeks with a standard deviation (SD) of 40;
- Cyp-A: a total of 68 patients is needed to detect a difference in means of 1.4 units between the two treatment arms at 24 weeks with a standard deviation (SD) of 2.0.

For ALSFRS-R, the software <http://hedwig.mgh.harvard.edu/biostatistics/node/42> shows the variance parameters which are from the Celebrex Study.

The variance of the random effects is the matrix 31.8 (intercept), 0 .6687 (slope) with a covariance of 0.8527. The error has a variance of 2.7.

With 142 patients enrolled, we will have 80% power to detect a 43% decrease in the rate of progression in ALSFRS over 6 months, at a two sided $p=0.05$ significance level. The study is also powered (in this case $p=0.05$ two sided) to show an absolute 25% reduction in the proportion of patients becoming non self-sufficient at 24 weeks, using a validated outcome measure with strong clinical significance (Marin, B. et al. 2015). In two studies from our group (Beghi, E. et al 2013; Chiò, A. et al. 2010) the average proportion of patients becoming non self-sufficient after 24 weeks in the placebo arm was 85%.

11.2 Statistical Analysis Plan

The study will use a modified intent to treat approach with all patients included who took at least one dose of the study medication or placebo. The primary analysis, described below, is valid as long as the probability of non-observation of a data point is independent of the value that would have been observed conditional on the previous observed data. In the case of ALSFRS this method has been shown to be robust (Ref <http://www.ncbi.nlm.nih.gov/pubmed/22987690>). Separate analyses will be performed in: 1. All randomized subjects receiving at least one dose of study medication (Intention-to-treat population); 2. Study completers: subjects completing the 12-month follow-up; 3. Study completers and compliers: subjects completing the 12-month follow-up and taking at least 75% of assigned dose. 4. All randomized subjects excluding protocol deviations (Per protocol, PP population). Descriptive statistics will be performed comparing the two treatment groups and safety of RNS60 and placebo. Continuous variables will be described using mean and standard deviation or median and interquartile range; categorical variables will be described as counts and percentages.

Biomarkers analysis:

The primary analysis will be a repeated measures analysis of variance (ANOVA) with a treatment variable that is the same for all treatments at baseline and then differs at later observation times. We will use an unstructured variance covariance matrix. The contrast of interest will depend on the outcome. Note that this is more general than a random effects model in situations where the observation times are fixed. For biomarkers that progress over time such as Cyp-A, the primary analysis will compare the rate of change in the biomarker over time in the placebo and active treatment groups. In biomarkers that do not progress but rather are elevated in patients, the primary analysis will be a comparison in the treatment effect. Both of these analyses are contrasts in a repeated measures ANOVA, the former by treatment \times time, and the latter being treatment \times (time>0). Each biomarker will be analyzed separately.

Efficacy analysis:

The numerical change of FVC, ALSFRS-R and ALSAQ-40 during the treatment and follow-up period will be assessed using repeated measures ANOVA, with an unspecified variance covariance matrix. The hypothesis will be tested using the time*treatment interaction which measures differences in the slope of the ALSFRS-R. Survival (time to death or tracheostomy) and time to functional disability (i.e., to reach a non self-supporting status or death or tracheostomy) will be assessed using actuarial methods with death and non-self supporting status as end-points. Survival will be described with the Kaplan-Meier method. Differences between the two treatment groups will be compared using the log-rank test. The statistical significance will be set at the 0.05 level for a two-tailed test.

The repeated measures ANOVA will use all available data, using Maximum Likelihood methods as suggested by (<http://www.nap.edu/read/12955/chapter/1>).

Safety analysis will be performed in all subjects receiving at least one dose of the experimental drug. All AEs, SAEs and AEs leading to treatment discontinuation will be recorded, listed and compared in the two treatment arms at any follow-up visit and at the end of the study. The number of patients reporting at least one AE or SAE will be compared between the treatment arms using the fisher exact test. The total number of AE and SAE will be compared between the treatment arms using a poisson model. MedDRA code system will be used for all recorded AE/SAE.

Given the exploratory value of this study, multiple comparison adjustments for Type I errors will not be considered as a more conservative significance level would lead to miss any potential treatment effect. Furthermore, if there is a suggestive benefit ($p<0.1$) in the clinical measures and several of the biomarkers, this will be considered sufficient evidence for further study.

If at the end of the patient enrolment period less than 50% of patients are enrolled, an interim-analysis will be performed to decide whether or not to continue the trial.

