2.3 Primary Endpoint

The mean change over time in the proportion of T-reg (measured via FOXP3 and CD25 mRNA); the mean change over time in the plasma concentrations of Cyp-A, 3-NT, Actin-NT, MCP-1, IL-17 in the two treatment arms, during the entire treatment period (from baseline to 24 weeks).

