3 STUDY DESIGN

The study is a multicenter, randomized, double-blind, placebo-controlled, parallel group, add-on pilot trial in patients taking riluzole. Patients diagnosed with ALS who meet the study's inclusion and exclusion criteria and sign the Informed Consent Form (ICF) will be enrolled. There will be two groups making up a total of 142 subjects: Group A (71 subjects) and Group B (71 subjects). Subjects will be randomly assigned to receive treatment with either RNS60 or placebo while concomitantly taking riluzole (50 mg twice a day). RNS60 or placebo will be administered intravenously once a week as well as inhaled via nebulization every morning (6 days a week on non-infusion days) for 24 weeks. All visit windows (± 1 or $+ 4$ days according to study procedure) are consecutive calendar days and are calculated from the day the participant starts study treatment (the day of the Randomization-Baseline Visit).

Blood samples will be collected five times for enrolled subjects to measure biomarkers. The first blood sample collection will be at baseline before the first infusion dose. Safety and efficacy will be assessed by way of physical exam, vital signs and AEs. Changes in disability and quality of life will be assessed using the ALSFRS-R scale, FVC and ALSAQ-40 scale. The overall treatment duration will be 24 weeks. Each subject will be followed up for a maximum period of 48 weeks (24-week treatment + 24-week follow up) or until death or tracheotomy, whichever occurs first.

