6.11 Premature Subject Withdrawal

The duration of the study includes 24 weeks of treatment plus 24 weeks of follow up. Subjects may voluntarily withdraw from the study or can be dropped at the discretion of the investigator at any time. Subjects must be withdrawn from the study if any of the following occurs:

- Unwillingness to comply with procedures as outlined in the study protocol;
- Withdrawal of consent;
- Loss to follow-up;
- Repeated non-compliance to dosing regimen or visit schedule (intake of 50% of recommended dose or less in three consecutive intervals between visits);
- Intolerable adverse events which may or may not be related to study medication and, if deemed drug-related, non remitting with down titration;
- Death/Tracheostomy;
- Requirement of medication doses greater than those allowable in the study;
- Abnormal laboratory value(s) deemed of medical concern;
- Administrative problems;
- Female becoming pregnant;
- Severe protocol deviations (at the Study Coordinator judgment).

If a subject withdraws or fails to return for visits, the investigator must determine the primary reason for the subject's premature withdrawal from the study, and record this information on the study-completion visit. Subjects must return all unused/remaining study drug to the investigative site. For subjects who are lost to follow up, the investigator should show "due diligence" by documenting in the source documents the steps taken to contact the subject, e.g., dates of telephone calls, registered letters, etc. Subjects who are prematurely withdrawn from the study will not be replaced.

Discontinued use of riluzole during the treatment period implies the discontinuation of the experimental drug. The subject will undergo a final safety evaluation and data collected up to the time of drug discontinuation will be used in the data analysis.

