11.3 Compliance

The compliance with the assigned at-home treatment will be measured by counting the number of used/unused syringes returned by the patient at each visit. A subject will be considered non-compliant if the amount of unused drug exceeds 25% of the assigned drug. The intake of less than 50% of the total amount of nebulized drug for 3 consecutive visits or in the event that the infusion is not performed for 2 consecutive visits implies withdrawal from the study.

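### Section 11.2 ties the completer and completer-complier sets to a 12-month follow-up that the 48-week schedule lacks, which on a plain reading removes survival events and selects on weeks 24 to 48 for a 24-week endpoint

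*Combined protocol and SAP*

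**What the plan says.** Section 11.2 takes as its main approach a "modified intent to treat approach with all patients included who took at least one dose of the study medication or placebo". It then announces separate analyses in four sets. Set 2 is "Study completers: subjects completing the 12-month follow-up". Set 3 is "subjects completing the 12-month follow-up and taking at least 75% of assigned dose". No endpoint is exempted from any set; only safety is given its own population.

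On timing, section 3 states "Each subject will be followed up for a maximum period of 48 weeks", made up of 24 weeks of treatment and 24 of follow-up, "or until death or tracheotomy, whichever occurs first". The last column of scheduled visits in Table 2 is week 48. Section 6.11 introduces a list with "Subjects must be withdrawn from the study if any of the following occurs", and death/tracheostomy is on that list. Under section 6.10, stopping study drug early also counts as withdrawal.

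The primary endpoint in section 2.3 is the change in the biomarkers "during the entire treatment period (from baseline to 24 weeks". Deaths or tracheostomies over the whole study are themselves a secondary endpoint (section 2.4, item 4). They also count as events in the time-to-disability analysis of section 11.2.

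On dose, section 11.3 says that compliance with home treatment is "measured by counting the number of used/unused syringes returned by the patient at each visit". The same section withdraws a patient whose infusion is missed at two consecutive visits. Section 6.1 has the infused volume recorded.

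**The concern.** There are three linked problems in sets 2 and 3.

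First, the membership rule names a time point that no patient reaches, so whoever programs the sets must guess what was meant.

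Second, if completion means reaching the last visit, the rule selects on an outcome of the trial. Survival in these sets then has nothing to analyse. Time to disability loses its fatal and tracheostomy events, and with them the disability events of patients who later die.

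Third, a comparison that closes at week 24 is restricted by what happens in the following 24 weeks, after treatment has ended. A patient with every biomarker sample through week 24 who leaves at week 40 is discarded. If treatment affects survival or retention, the remaining groups are no longer comparable as randomized.

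The stakes are modest but real. Section 11.2 makes no multiplicity adjustment, and it treats a suggestive result (p below 0.1) in the clinical measures and several biomarkers as enough for further study. It does not say which analysis set that judgement uses, so a result from a selected set could enter it.

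**Working it through.** **1. Is there a 12-month time point?** 48 weeks × 7 / 30.4375 = 11.04 months. A year is 365.25 / 7 = 52.18 weeks, so the last visit falls about 4.2 weeks short. Neither section 3 nor Table 2 has a later visit.

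**2. Can a patient with a survival event be a completer?**
- Section 3: follow-up stops at death or tracheostomy.
- Section 6.11: death/tracheostomy is a mandatory withdrawal.
- Section 11.2: members of sets 2 and 3 must complete follow-up.

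A withdrawn patient would not normally be called a completer. On that reading the number of deaths and tracheostomies in sets 2 and 3 is 0 in each arm. The cumulative proportion is 0% in both arms and the log-rank test has no events to compare.

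**3. How many patients does the later milestone cost a 24-week comparison?** Inputs: 142 randomized, and drop-out of 1.75% per month, described as 10% over the study (section 11.1).

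Reproducing the plan's figure: 1 − (1 − 0.0175)^6 = 0.1005. The stated 10% therefore corresponds to about six months.

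Remaining patients, N(m) = 142 × 0.9825^m:

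| Time point | Months | Lost | Remaining |
|---|---|---|---|
| Week 24 | 5.52 | 9.3% | 128.8 |
| 6 months | 6 | 10.05% | 127.7 |
| Week 48 | 11.04 | 17.7% | 116.9 |

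The difference is 127.7 − 116.9 = 10.8 to 128.8 − 116.9 = 11.9. So about 11 or 12 patients would leave the set for reasons arising after the primary endpoint is complete. This assumes that the monthly rate holds to week 48, which the plan does not say.

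The alternative is to take 10% as the loss over all 48 weeks, at a constant rate. Then 142 × 0.9 = 127.8 remain at week 48. Week 24 is half of that time, so 142 × √0.9 = 134.7 remain there, and about 7 patients (134.7 − 127.8 = 6.9) are lost in between. The range is therefore about 7 to 12 patients.

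**4. What does 75% of assigned dose mean?** The assigned treatment has two routes: one infusion a week, and two syringes a day on six days a week. Over 24 weeks that is 24 infusions and 24 × 6 × 2 = 288 syringes. A patient who misses every other infusion never misses two in a row, so the withdrawal rule in 11.3 is not triggered. That patient receives 12/24 = 50% of infusions, and 288/288 = 100% of syringes if all are used. Whether this is a complier depends on how the routes are combined, and the visible text gives no percentage rule for infusions.

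**The case against.** The strongest reply is that little depends on these sets. The trial is an exploratory pilot, its main approach is modified intention-to-treat, and the repeated-measures model uses all available data by maximum likelihood. That stands, and it limits the severity.

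It can also be said that 12 months is shorthand for the final visit, and that one study-wide completer set suits the endpoints that run through follow-up. Both are fair. A reader might infer from the literal wording that the sets will be empty, but the schedule makes week 48 the evident intention. The wording needs correcting all the same.

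Next, section 3 describes follow-up as 48 weeks or until death or tracheostomy, so a patient who dies might be regarded as having completed it. This is arguable. Section 6.11 points the other way, and the plan does not resolve the matter. Exclusion of these patients is therefore a strong inference and not a stated rule.

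A reader might also infer that compliance ignores infusions. The documents do not support that. Section 11.2 refers to the assigned dose without limiting it to one route, the syringe count in 11.3 concerns home treatment, and 11.3 has a rule for missed infusions. Section 6.14 on treatment compliance is removed from the public text, so its content cannot be held against the plan.

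Finally, a reader might infer a breach of the planned power. Section 11.1 makes no power claim for completer sets, so there is none to breach.

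**Conclusion.** The point holds for the definition of sets 2 and 3. The 12-month milestone conflicts with the 48-week schedule. On the plain reading of sections 3 and 6.11, survival in these sets has no events and time to disability loses its fatal ones. For the baseline-to-week-24 biomarker endpoint, the rule discards patients with complete week-24 data and selects on post-treatment events. If 1.75% per month continues to week 48, about 117 of 142 remain against about 128 to 129 at week 24. The plan does not say whether its drop-out rate includes deaths, so no separate allowance is made for them. The selection matters more than the loss of numbers.

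The modified intention-to-treat analysis is untouched, and nothing here suggests that the trial's main result would be biased. The unclear 75% rule is a minor matter of clarification.

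**What to change.** In section 11.2:

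- Replace the 12-month milestone with week 48 for endpoints that run through follow-up.
- For the biomarker analyses and other analyses that close at week 24, define completers by completion of week 24. This still leaves out patients who die or withdraw before then, so the results should be read as supportive.
- Do not run survival or time to disability in sets 2 and 3; report them in the modified intention-to-treat set only.
- As a minor clarification, state how 75% of assigned dose is calculated across infusions and syringes, or refer to section 6.14 if it already does so.

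The cost is a few sentences in the analysis plan and a small programming change. Visit dates, infused volumes and syringe counts are already collected.

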2.4 Secondary Endpoints

1. The mean change in the proportion of T-reg (measured via FOXP3 and CD25 mRNA); the mean change over time in the plasma concentrations of Cyp-A, 3-NT, Actin-NT, MCP-1, IL-17 during the follow up period (from 24 to 48 weeks);
2. The cumulative proportion of subjects becoming no longer self-sufficient at 4, 12, 24, 36 and 48 weeks in the two treatment arms (defined as those scoring 2 or lower on at least one of the ALSFRS-R items for swallowing, cutting food and handling utensils, or walking);
3. The mean change of ALSFRS-R total score in the two treatment arms during the treatment and follow up period;
4. The cumulative proportion of deaths or tracheostomies in the two treatment arms during the entire study including follow-up;
5. The mean change of FVC score in the two treatment arms during the treatment and follow up period;
6. The total number of subjects in the two treatment arms experiencing at least one AE leading to treatment discontinuation at 4, 12 and 24 weeks;
7. The mean number of AEs per treatment arm at 4, 12, 24 and 48 weeks;

8. The mean change of ALSAQ-40 score measuring quality of life at the completion of the treatment and follow up period.

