4.2 Inclusion Criteria

- 1) Age 18 through 80 years inclusive;

- 2) Geographically accessible to the site and able to come to the site center once a week for 24 weeks;
- 3) “Definite” or “Probable” or “Probable laboratory-supported” ALS diagnosis according to the revised El Escorial criteria;
- 4) Disease duration 6 to 24 months from symptom onset to study entry;
- 5) Self sufficiency: Satisfactory bulbar and spinal function (score 3+ on the ALSFRS-R for swallowing, cutting food and handling utensils, and walking);
- 6) Satisfactory respiratory function (FVC \geq 80% of predicted);
- 7) Documented progression of symptoms in the last three months as measured by the ALSFRS-R scale (decrease of at least one point);
- 8) Ability to understand and comply with the study requirements;
- 9) Ability to give written informed consent personally or, as an alternative, via a legally authorized representative;
- 10) Treatment with riluzole 50 mg twice/day for at least 1 month prior to screening visit;

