6.7 Treatment Arms

142 patients with ALS will be randomized in 2 parallel groups, in a ratio of 1:1. One group will be treated with RNS60 and one group will be treated with placebo.

Group A	RNS60 375 mL IV once a week + RNS60 4 mL inhaled once a day (six days/week) + Riluzole 50 mg twice a day
Group B	NS 375 mL IV once a week + NS 4 mL inhaled once a day (six days/week) + Riluzole 50 mg twice a day

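### The log-rank test for time to functional disability names no strata, although patients enter one or two points from the event: a valid test that could be made more efficient at no cost

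*Combined protocol and SAP*

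**What the plan says.** - Entry (4.2, item 5) requires "score 3+ on the ALSFRS-R for swallowing, cutting food and handling utensils, and walking".
- The event (2.4, item 2) covers patients "defined as those scoring 2 or lower on at least one of the ALSFRS-R items", and the items listed are the same three.
- Table 2 schedules the ALSFRS-R at screening and on Day 1, before treatment, and then at weeks 4, 12, 24, 36 and 48.
- Section 6.6 describes permuted blocks of 4 and names no stratification by function. On size, 6.7 says "142 patients with ALS will be randomized in 2 parallel groups, in a ratio of 1:1".
- Section 11.2 analyses time to non-self-supporting status, death or tracheostomy: "Differences between the two treatment groups will be compared using the log-rank test". On the level, "The statistical significance will be set at the 0.05 level for a two-tailed test". It names no strata or covariates.
- Section 11.1 adds: "The study is also powered" (two-sided 0.05) "to show an absolute 25% reduction in the proportion of patients becoming non self-sufficient at 24 weeks". The basis is two earlier trials in which "the average proportion of patients becoming non self-sufficient after 24 weeks in the placebo arm was 85" per cent. No power level is given for this outcome.
- Section 4.1 says bulbar-onset and spinal-onset cases will be looked at separately in the analysis. Section 11.2 does not take this up.

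**The concern.** The baseline value at issue is the starting score on the very items that define the event. A patient with any item at 3 reaches the event with a one-point drop. A patient with all three at 4 needs a two-point drop on one item. Some difference in risk between these groups is therefore built into the definition.

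Pooling groups with unequal hazards weakens a log-rank comparison. The high-risk patients leave the risk set first, and they leave faster in the arm that does worse, so the arms look more alike over time than they are within each group. A chance imbalance in starting scores also carries straight into the comparison.

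At stake is sensitivity on a clinical outcome that 11.1 singles out. Under 11.2, benefit at p<0.1 in the clinical measures together with several biomarkers would justify further study.

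**Working it through.** **1. The plan's own claim.** Inputs: 85% v 60% at week 24, two-sided 0.05, 71 per arm. The 10% dropout is stated in 11.1 for the Cyp-A calculation. Applying it here, which leaves 64 per arm, is an assumption.

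Power = Φ{[|p1−p2|√n − 1.96√(2p̄q̄)] / √(p1q1+p2q2)}, with p̄ = 0.725, √(2p̄q̄) = √0.39875 = 0.6315 and √(0.1275+0.24) = 0.6062.

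- n = 71: (0.25×8.426 − 1.238)/0.6062 = 1.433, so power is 92.4%.
- n = 64: (0.25×8 − 1.238)/0.6062 = 1.257, so power is 89.6%.

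On the hazard scale, with exponential times, HR = ln 0.40/ln 0.15 = 0.483. Schoenfeld's formula needs 4(1.96+0.842)²/(ln 0.483)², or 60 events for 80% power. Expected events by week 24 are 64×1.45 = 93 to 71×1.45 = 103, giving 94-96% power. The statement that the study is powered for this outcome is supported.

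**2. What has to be assumed.** The documents do not give the item maximum (4 is assumed), the share of patients entering with an item at 3, or how much sooner those patients reach the event. Each pair of stratum risks below averages 85% on placebo, and HR = ln(1−risk near)/ln(1−risk far):

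- 89%/81%, half near the event: ln 0.11/ln 0.19 = 1.3
- 95%/75%, half near: ln 0.05/ln 0.25 = 2.2
- 97%/73%, half near: ln 0.03/ln 0.27 = 2.7
- 97%/67%, 60% near: ln 0.03/ln 0.33 = 3.2

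**3. Power, plain v stratified log-rank, by simulation.** Event times are exponential and events are detected at visits.

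Week 24, 64 per arm, 3,000 runs (a range is the spread over repeat simulations):

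| Effect | Between-stratum HR | Plain | Stratified |
|---|---|---|---|
| 25 points | 2.7 | 95% | 97.5-98% |
| 20 points | 2.7 | 84-86% | 91-92% |
| 15 points | 1.3 | 60-61% | 60-61% |
| 15 points | 2.2 | 63% | 68-69% |
| 15 points | 2.7 | 65% | 73-74% |
| 15 points | 3.2 | 66-68% | 78-80% |
| 10 points | 2.7 | 37-38% | 45-47% |

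Week 48, 71 per arm, dropout 1.75% per month, 30-70% near the event, 2,500 runs (simulation error about 0.8 points near 80%), 85% v 68% at week 24:

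| Between-stratum HR | Plain | Stratified | Change in points |
|---|---|---|---|
| 1 | 78-80% | 78-79% | −0.1 to −0.8 |
| 1.5 | 78-79% | 79-80% | 0.7 to 1.2 |
| 2 | 79-80% | 83-84% | 3.5 to 4.8 |
| 3 | 80-83% | 89-92% | 7.3 to 10.1 |
| 4 | 81-86% | 92-96% | 9.8 to 14.1 |

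In the same set-up, 85% v 60% gives 97-99% plain and 97-100% stratified.

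The mechanism shows in the hazard ratios. With no stratum difference, 85% v 68% corresponds to ln 0.32/ln 0.15 = 0.60. With half the patients near the event and a between-stratum HR of 3, the same proportions come from a within-stratum treatment HR of 0.53.

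**4. Type I error.** Over randomisation, with no drug effect and between-stratum HRs of 1, 2 and 4, the plain test rejects 4.8%, 5.5% and 4.9% of the time, and the stratified test 5.1%, 5.4% and 4.9%.

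**5. Chance imbalance.** If half the patients start near the event, the between-arm difference in that share has SD √(2×0.5×0.5/71) = 8.4 points, so a 95% range of about ±16. At HR 2-3 the stratum risks differ by about 18-26 points, so a 16-point imbalance moves the week-24 proportion by 0.16×18 to 0.16×26, or about 3-4 points. With the imbalance fixed at 37 v 27 of 64 (15.6 points) and no drug effect, the plain test rejects 8.4-8.8% of the time and the stratified test 4.8-5.2%.

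**The case against.** The case for leaving the plan alone is substantial. At the effect for which 11.1 claims power, stratifying gains 0-3 points. The larger gains come at effects for which the plan claims nothing. The quantity that drives them, how prognostic the Day 1 item status is, appears nowhere in the documents, and with a weak relation the gain vanishes. An unstratified log-rank that matches unstratified randomisation is conventional. The choice of strata is partly a preference: the number of items at 3, or the lowest score as a Cox covariate, would also serve. The outcome is secondary in a pilot that the protocol calls exploratory. Section 4.1 already names another grouping, onset type, which may overlap because swallowing is one of the three items.

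All of this limits the weight of the point, and most of it stands. It does not remove the point, because the change costs almost nothing and the documents themselves tie the baseline variable to the event. Onset type is a different variable, and 11.2 gives it no role in this test.

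A reader might infer two stronger things, and neither is supported. One is that the planned test has an inflated type I error. The rate of 8-9% holds only given an imbalance of roughly two SD; over randomisation the rate is about 5%. The other is that the power claim in 11.1 fails. It holds under either test.

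**Conclusion.** The planned analysis is valid, and the plan's 25-point target is well covered. What holds is a loss of efficiency at smaller effects, plus avoidable exposure to chance imbalance in starting scores. For 15- to 17-point effects the gain from stratifying is about 0-1 points of power at a between-stratum HR of 1.3-1.5, about 3-7 at 2-2.2 (the runs gave 3.5 to 6, widened for simulation error), and about 7-12 at about 3.

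These figures rest on assumed stratum shares and risks, exponential event times, and 4 as the item maximum. That 11.2 names no strata, and that entry and event share the same items, can be read directly from the text. The size of the gain cannot. This is a free improvement, not a defect that threatens the trial's conclusions.

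**What to change.** In 11.2, prespecify for time to functional disability:

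- a log-rank test stratified by Day 1 item status (any of the three items at 3 v all at 4);
- a hazard ratio from a Cox model stratified the same way;
- a Cochran-Mantel-Haenszel test on the same strata for the 24-week proportion, which is the quantity in the 11.1 power statement and has no named test in 11.2;
- how this combines with the bulbar/spinal grouping in 4.1, for example onset type as a covariate in the Cox model.

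The wording should be fixed before unblinding, since strata chosen after an imbalance is seen would not be credible. The cost is a few lines of text. No data, visits or patients are added, and the power given up if the strata prove weakly prognostic is about 1 point or less.
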